9.5.1.6.1 ADVERSE EVENTS AND EVENTS ASSOCIATED WITH SPECIAL SITUATIONS

An AE is any untoward medical occurrence in a patient or clinical investigation subject administered an investigational product. An AE does not necessarily have a causal relationship with the medicinal product. For this study, the study drugs are eribulin mesylate and pembrolizumab.

The criteria for identifying AEs in this study are:

- Any unfavorable and unintended sign (including an abnormal laboratory finding), symptom, or disease temporally associated with the use of an investigational product, whether or not considered related to the investigational product (Note: Every sign or symptom should not be listed as a separate AE if the applicable disease [diagnosis] is being reported as an AE).
- Any new disease or exacerbation of an existing disease. However, worsening of the primary disease should be captured under efficacy assessments as disease progression rather than as an AE.

- Any deterioration in nonprotocol-required measurements of a laboratory value or other clinical test (eg, ECG or x-ray) that results in symptoms, a change in treatment, or discontinuation of study drug.
- Recurrence of an intermittent medical condition (eg, headache) not present pretreatment (Baseline).
- An abnormal laboratory test result should be considered an AE if the identified laboratory abnormality leads to any type of intervention, withdrawal of study drug, or withholding of study drug, whether prescribed in the protocol or not.

All AEs observed during the study will be reported on the Adverse Event CRF. All AEs, regardless of relationship to study drug or procedure, should be collected beginning from the time the subject signs the study ICF and for 30 days after the last dose of study treatment. SAEs will be collected for 90 days and ECIs will be collected for 30 days after the last dose or 30 days following the last dose if the subject initiates new anticancer therapy, whichever is earlier. An AE will not be reported on the Adverse Event CRF if other anticancer treatment is started. All SAEs will be reported on the Adverse Event CRF.

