6.2.6 Prior and Concomitant Therapy

All investigator terms (verbatim terms) for medications recorded in the CRF will be coded to an 11-digit code using the World Health Organization Drug Dictionary (WHO DD, version WHODDMAR18_HD_B2) drug codes. The number (percentage) of subjects who took prior or concomitant medications will be summarized on the FAS by Anatomical Therapeutic Chemical (ATC Level 1) class, Pharmacological (ATC Level 3) Class and WHO DD preferred term. Prior medications will be defined as medications that stopped before the first dose of study drug. Concomitant medications will be defined as medications that (1) started before the first dose of study drug and were continuing at the time of the first dose of study drug, or (2) started on or after the date of the first dose of study drug up to 30 days (90 days if given for adverse events) after the subject's last dose. A listing of prior and concomitant medications will be included in the clinical study report for this protocol.

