6.6.3 Adverse Events

All Adverse Events (AE) will be graded by the investigators using CTCAE v4.03. The AE verbatim descriptions (investigator terms from the CRF) will be classified into standardized medical

terminology using the Medical Dictionary for Regulatory Activities (MedDRA). Adverse events will be coded to the MedDRA (Version 22.0) lower level term (LLT) closest to the verbatim term. The linked MedDRA preferred term (PT) and primary system organ class (SOC) are also captured in the database.

The incidence of TEAEs will be summarized descriptively. A TEAE is defined as an AE that emerged during treatment or up to 30 days (90 days for SAEs and /or events of clinical interest) following last dose of study drug, having been absent at pretreatment (Baseline) or

- Reemerged during treatment or up to 30 days (90 days for SAEs and /or events of clinical interest) following last dose of study drug, having been present at pretreatment (Baseline) but stopped before treatment, or
- Worsened in severity during treatment or up to 30 days (90 days for SAEs and /or events of clinical interest) following last dose of study drug relative to the pretreatment state, when the AE was continuing.

Per protocol amendment 1, Events of clinical interest (ECI) for this trial include: an elevated aspartate aminotransferase (AST) or alanine aminotransferase (ALT) lab value that is greater than or equal to $3 \times$ ULN and an elevated total bilirubin lab value that is greater than or equal to $2 \times$ ULN and, at the same time, an alkaline phosphatase lab value that is less than $2 \times$ ULN, as determined by way of protocol-specified laboratory testing or unscheduled laboratory testing.

We used the following AE PT terms to identify ECI above:

- ALT increased
- AST increased
- Blood bilirubin increased
- Blood alkaline phosphatase increased

Only those AEs that are treatment emergent will be included in summary tables. All AEs, treatment emergent or otherwise, will be presented in subject data listings.

An overview table, including the incidence of and the number of subjects with TEAEs, TEAEs with grade 3 or above, serious adverse events (SAEs), deaths, and TEAEs that led to death, treatment discontinuation, dose reduction, or dose interruption will be provided.

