2. If a subject did not have PD or death, the censoring date will be the earliest censoring date if the subject met multiple censoring criteria (No. 1, No. 3, No. 4, No. 7).

Rules for missing dates:

In case of dates missing in adverse event and concomitant medication collection following rules will be followed.

- **Adverse Events**

Adverse Events with incomplete start dates will be considered treatment emergent if:

- a. Day and month are missing and the year is equal to or after the year of the first dose date;
- b. Day is missing, and the year is after the year of the first dose;
- c. Day is missing and the year is equal to the year of the first dose date and the month is equal to or after the month of the first dose date;
- d. Year is missing; or
- e. Complete date is missing.

- **Concomitant Medications**

Medications will be considered concomitant if:

- a. Day and month are missing and the year is equal to or after the year of the first dose date;
- b. Day is missing, and the year is after the year of the first dose;
- c. Day is missing and the year is equal to the year of the first dose date and the month is equal to or after the month of the first dose date; or
- d. Year is missing; or complete date is missing.

Pharmacokinetics/Pharmacodynamic Data Handling

- **Lower Limit of Quantification of Eribulin Plasma Concentration**

The Lower Limit of Quantification (LLOQ) of eribulin plasma concentration is 0.200 ng/mL.

- **Below Limit of Quantification Handling for Calculation of Pharmacokinetic Parameters**

While calculating PK parameters in Phoenix/WinNonlin, BLQ values will be handled according to the [NCA-MNL](#).

- **BLQ Handling for Developing Concentration-Time Profiles**

When developing individual concentration-time profiles, BLQ values will be handled according to the [NCA-MNL](#).

- **Handling of Anomalous Concentration Values**

The handling of anomalous concentration values will follow the guidance in the [NCA-MNL](#).

- **General Rules for Presentation of Drug Concentrations and PK Parameters**

When presenting individual/raw (raw, hereafter) values and summary statistics, the following rule will be applied: for drug concentrations and concentration-dependent pharmacokinetic parameters, all summary statistics (mean, median, geometric mean, SD, and CV) will have 3 significant digits. For t_{max} and t_{lag} , raw values and median have fixed 2 decimal places.

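### The SAP's missing-date rule for adverse events ignores the stop date, so a screening event known to have ended before the first dose can be counted as treatment-emergent

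*SAP*

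**What the plan says.** SAP Section 8, under the rules for missing dates, opens with an instruction that carries no exception: "In case of dates missing in adverse event and concomitant medication collection following rules will be followed".

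For adverse events it then says "Adverse Events with incomplete start dates will be considered treatment emergent if" any of these holds:

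- (a) day and month are missing and the year is that of the first dose or later;
- (b) the day is missing and the year is later than that of the first dose;
- (c) the day is missing, the year is that of the first dose, and "the month is equal to or after the month of the first dose date";
- (d) the year is missing;
- (e) the whole date is missing.

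The medication list uses the same patterns. It begins "Medications will be considered concomitant if" and ends "Year is missing; or complete date is missing". Unlike the adverse-event list, it does not name the date being tested.

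SAP 6.6.3 defines a treatment-emergent event as one that arises, returns or worsens during treatment or within 30 days of the last dose (90 days for serious events and events of clinical interest). Protocol 9.7.1.8.2 likewise asks for onset or worsening on or after the first dose. SAP 6.6.3 admits only treatment-emergent events to the summary tables; listings show all events.

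SAP 6.2.6 says: "Prior medications will be defined as medications that stopped before the first dose of study drug".

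**The concern.** Protocol 9.5.1.6.1 says that all adverse events "should be collected beginning from the time the subject signs the study ICF", and Protocol 9.1.1 places screening on Day -21 to Day -1. Events that begin and end before the first dose are therefore in the database by design. If such an event has an incomplete start date but a known stop date before dosing, its status is not in doubt: it cannot have arisen, returned or worsened on treatment. Section 8 nevertheless declares it treatment-emergent. The SAP then gives two answers for one record, and the wrong one feeds the incidence tables. What is at stake is the accuracy of some low-frequency rows in the safety tables and the consistency of the SAP with its own definition.

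**Working it through.** The plan states no figure on this point, so the check applies the rule to test records and then sizes the effect.

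**Step 1: apply items (a) to (e).** Take an illustrative first dose on 15 March 2017 and an event with a recorded stop date of 10 March 2017, five days earlier. Under SAP 6.6.3 this record cannot be treatment-emergent.

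| Recorded start | Item met | Section 8 | SAP 6.6.3 | With a stop-date check |
|---|---|---|---|---|
| March 2017, day missing | (c) | emergent | not emergent | not emergent |
| 2017, day and month missing | (a) | emergent | not emergent | not emergent |
| Year missing | (d) | emergent | not emergent | not emergent |
| Whole date missing | (e) | emergent | not emergent | not emergent |
| February 2017, day missing | none | not emergent | not emergent | not emergent |

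Four of the five patterns are misclassified, and a stop-date check corrects all four. Item (b) cannot catch a pre-dose onset, because it needs a year after that of the first dose.

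**Step 2: how often a pre-dose onset meets each item.** Assume onsets spread evenly over Day -21 to Day -1 and first doses spread evenly over 2016 to 2018. That is 1,096 days × 21 = 23,016 combinations.

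- Item (c) misses an onset only if it falls in an earlier month than the first dose. Each start of a month contributes 21 + 20 + … + 1 = 231 such combinations. Over 36 months that is 8,316. Share flagged: 1 − 8,316/23,016 = 0.639, about 64%.
- Item (a) misses an onset only if it falls in an earlier year: 3 × 231 = 693. Share flagged: 1 − 693/23,016 = 0.970, about 97%.
- Items (d) and (e) flag 100%.

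These shares cover all pre-dose onsets. Events that have already ended by the first dose tend to have begun earlier, so for them the 64% is probably somewhat high.

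**Step 3: size.** The 170 subjects come from the protocol and SAP. The other inputs are assumptions: 0.3 to 0.5 screening events per subject, 5% to 10% of them with a partial start date, and half of those over before dosing.

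- If every partial date is flagged: low 170 × 0.3 × 0.05 × 0.5 = 1.3; high 170 × 0.5 × 0.10 × 0.5 = 4.3.
- If every partial date lacks only the day, multiply by 0.64: 0.8 to 2.7.

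One extra subject changes a term's incidence by 1/170 = 0.6 percentage points.

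**The case against.** The best defence is that treating doubtful onsets as treatment-emergent is a normal conservative convention in safety reporting. That stands where the record leaves doubt. It does not cover a record whose stop date settles the matter.

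SAP Section 9 places derivation rules in separate programming documents, and a stop-date check may be there. The documents do not show one, and a specification that added it would depart from the SAP's unconditional rule. This means only that the tables could be overstated, not that they will be.

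SAP 6.6.3 counts a subject once per system organ class and preferred term. A false event therefore adds nothing where the subject also has a true treatment-emergent event of that term. This stands and lowers the effect further.

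A reader might go further in three ways that the text does not support.

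- *That the medication tables contradict SAP 6.2.6.* This holds only if the medication list tests the start date, which it does not say. If it tests the stop date, a drug with a complete stop date before dosing is never caught and there is no conflict. A start-date reading also fits less well: a drug with a partial start in an earlier month and still in use meets none of the items, yet 6.2.6 makes it concomitant. What can be shown is an ambiguity. The documents also give no basis for a count of affected medications.
- *That the rule has no upper limit, so late events flood in.* Protocol 9.5.1.6.1 ends collection at 30 days for adverse events and 90 days for serious ones, or 30 days if new anticancer therapy starts. The main exception is related serious events, which Protocol 9.5.4.1 asks to be reported at any time.
- *That every event known to have ended before dosing is caught.* The fifth test record shows otherwise.

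**Conclusion.** The point holds for adverse events. On its plain text, Section 8 can class as treatment-emergent an event that SAP 6.6.3 excludes, when the start date is incomplete and the stop date precedes the first dose. This is a stated rule that gives a wrong result, not a missing detail. The consequence is minor: probably no more than a few events in 170 subjects. That figure rests wholly on assumed rates; only the number of subjects comes from the documents. Response rate, progression-free survival and overall survival do not depend on the rule. For medications the conclusion is narrower: the list must say which date it tests.

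**What to change.** - **Adverse events, SAP Section 8:** add to the list *unless the stop date (complete or partial) shows that the event ended before the first dose*. Leave the rule as it is for all other records, including those with no usable stop date.
- **Medications, same section:** name the date that the list tests. If it is the start date, add the same exception, so that a drug stopped before the first dose is prior, as SAP 6.2.6 requires.
- **Optional:** exclude records whose partial start date can only fall after the 30- or 90-day window. Few records should be affected.

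The cost is two or three sentences in the SAP and one extra condition in the derivation program. No new data are needed: the exception uses only stop dates already recorded.

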9 PROGRAMMING SPECIFICATIONS

The rules for programming derivations and dataset specifications are provided in separate documents.

10 STATISTICAL SOFTWARE

Statistical programming and analyses will be performed using SAS® (SAS Institute, Inc., Cary, NC, USA), version 9.3 or higher, and/or other validated statistical software as required. Non-compartmental analysis (NCA) will be performed using Phoenix 64 WinNonLin (version 7.0 or later).

11 MOCK TABLES, LISTINGS AND GRAPHS (TLGS)

The study TLG shells will be provided in a separate document, which will show the content and format of all tables, listings, and graphs in detail.

13 APPENDICES

13.1 Bayesian Stopping Boundaries

N	LB	UB	N	LB	UB	N	LB	UB
38	6	16	60	12	22	82	19	27
39	6	16	61	12	22	83	19	27
40	6	17	62	12	23	84	19	27
41	7	17	63	13	23	85	20	27
42	7	17	64	13	23	86	20	27
43	7	18	65	13	23	87	20	28
44	7	18	66	14	23	88	21	28
45	8	18	67	14	24	89	21	28
46	8	18	68	14	24	90	22	28
47	8	19	69	14	24	91	22	28
48	9	19	70	15	24	92	22	28
49	9	19	71	15	25	93	23	28
50	9	20	72	15	25	94	23	28
51	9	20	73	16	25	95	24	28
52	10	20	74	16	25	96	24	28
53	10	20	75	16	25	97	25	28
54	10	21	76	17	26	98	25	28
55	10	21	77	17	26	99	26	28
56	11	21	78	17	26	100	27	28
57	11	21	79	18	26			
58	11	22	80	18	26			
59	12	22	81	18	27			

Footnote:

N=number of subjects included in the predictive probability calculation;

LB=lower bound (futility boundary crossed if # objective response \leq LB);

UB=upper bound (efficacy boundary crossed if # objective response \geq UB).

SIGNATURE PAGE

Author:

Signature

PPD

